#### **9.4.2 Paravalvular Leak**

Paravalvular leak should be reported as an adverse event in the following cases:

- When paravalvular leak remains moderate or severe after balloon dilatation, or
- When valve-in-valve, surgical conversion or other intervention is required for any grade of paravalvular leak after implant.

#### **9.4.3 Reporting Unanticipated Adverse Device Effects**

An investigator shall submit to the Sponsor and the reviewing IRB a report of any unanticipated adverse device effect occurring during an investigation no later than three (3) calendar days from the day the site personnel first learns of the effect.

## 9.5 Classification of Causal Relationships

For each adverse event, the causal relationship between the adverse event and the Portico Transcatheter Heart Valve and Delivery System, and the causal relationship between the event and the index procedure, will be assessed by the Investigator and reported as such on the Adverse Event case report form. Final causal relationships for events related to primary and secondary endpoint criteria according to the Valve Academic Research Consortium (VARC 2) definitions will be determined per CEC adjudication.

## 9.6 Subject Death

Subject death is a potential outcome of a Serious Adverse Event that will be reported within three (3) calendar days from the time of the site personnel knowledge of the event, if the event occurs from the time of signed informed consent until the subject exits the study.

Subject death will be subdivided specifically denoting cardiovascular and non-cardiovascular mortality:

1. Cardiovascular mortality includes any one of the following criteria:
  - a. Any death due to proximate cardiac cause (such as MI, tamponade, worsening heart failure)
  - b. Sudden or unwitnessed death
  - c. Death of unknown cause
  - d. All procedure-related deaths including those related to a complication of the procedure or treatment for a complication of the procedure
  - e. Death caused by non-coronary vascular conditions such as cerebrovascular disease, pulmonary embolism, ruptured aortic aneurysm, dissecting aneurysm, or other vascular disease.
2. Non-cardiovascular mortality includes any death in which the primary cause of death is clearly related to another condition (e.g. trauma, cancer, suicide)

An Adverse Event CRF, Death CRF and relevant source documentation including the death certificate should be submitted to SJM.

## 10 Independent Boards (Pivotal IDE and CAP)

### 10.1 Clinical Events Committee

An independent Clinical Events Committee (CEC), consisting of, at a minimum, an interventional cardiologist, cardiologist, cardiothoracic surgeon, and a neurologist will adjudicate events related to primary and secondary endpoint criteria according to the Valve Academic Research Consortium (VARC 2) definitions. The CEC will have final adjudication responsibilities for subject outcomes related to primary and secondary endpoint criteria. Members of the CEC cannot be investigators on the PORTICO Clinical

Study. A charter that is agreed upon by both the Sponsor and the independent CEC governs the event adjudication process.

## **10.2 Data Safety Monitoring Board (DSMB) (Pivotal IDE)**

An independent Data Safety Monitoring Board (DSMB) will be utilized to regularly review study progress with regard to safety of the pivotal IDE trial. Members of the DSMB cannot be investigators on the PORTICO Clinical Study. Board membership may consist of, but not limited to, a cardiologist, cardiac surgeon, neurologists, and a biostatistician.

The primary responsibilities of the DSMB include:

- Review and validate the subject sample (i.e., review inclusion/exclusion deviations and other protocol deviations)
- Provide oversight for issues affecting general subject welfare
- Recommend premature study termination or modification of the trial for any perceived safety concerns

At any time during the course of the study, the DSMB may offer opinions or make formal recommendations concerning aspects of the study that impact subject safety (e.g., safety-related protocol changes or input regarding adverse event rates associated with the investigational study). Additionally, the DSMB may act as an advisory panel for questions regarding informed consent, subject enrollment, protocol implementation, study endpoints, data discrepancies, and other issues that may present during the course of the study. A charter that is agreed upon by both the sponsor and the DSMB members governs the role and responsibility of this committee.

The recommendations of the DSMB are not binding, and all final decisions related to modifications to the clinical investigational protocol rest with the Sponsor.

## **11 Statistical Methods and Analysis (Pivotal IDE)**

This section describes the statistical methods and analysis of the pivotal IDE randomized cohort unless otherwise specified. The analysis will be performed on combined high-risk cohort and extreme-risk cohort.

### **11.1 Analysis Populations**

The primary analysis will be based on the intention-to-treat (ITT) population. The ITT population is defined

[REDACTED]

Additional populations will be used to confirm the results of the ITT population.

[REDACTED]

[REDACTED]

## 11.2 Randomization and Stratification

[REDACTED]

## 11.3 Primary Endpoints

### 11.3.1 Primary Effectiveness Endpoint

The primary effectiveness endpoint is the composite endpoint of all-cause mortality or disabling stroke at one year. This endpoint will be evaluated by a non-inferiority test comparing the Portico test group to the control (CAV) group, and the primary analysis will be conducted on the ITT population.

[REDACTED]

[REDACTED]

[REDACTED]

[REDACTED]

[REDACTED]

[REDACTED]

[REDACTED]

[REDACTED]

[REDACTED]

[REDACTED]

[REDACTED]

[REDACTED]

[REDACTED]

[REDACTED]

[Redacted]

[Redacted]

### 11.3.2 Primary Safety Endpoint

The primary safety endpoint is the non-hierarchical composite endpoint of all-cause mortality, disabling stroke, life-threatening bleeding requiring blood transfusion, acute kidney injury requiring dialysis, or major vascular complications at 30 days. This endpoint will be evaluated by a non-inferiority test comparing Portico test group to the control group, and the primary analysis will be conducted on the ITT population.

[Redacted]

[Redacted]

[Redacted]

[Redacted]

[Redacted]

[Redacted]

[Redacted]

[Redacted]

[Redacted]

[Redacted]

[Redacted]

[Redacted text block]

[Redacted text block]

[Redacted text block]

[Redacted text block]

[Redacted text block]

[Redacted text block]

[Redacted text block]

[Redacted text block]

#### 11.4 Sample Size Calculations

[Redacted text block]

[Redacted text block]

[Redacted text block]

[Redacted text block]

[Redacted text block]

[Redacted text block]

[Redacted text block]

#### 11.4.1 Sample Size for the Primary Effectiveness Endpoint

[Redacted text block]

[Redacted text block]

[REDACTED]

**11.4.2 Sample Size for the Primary Safety Endpoint**

[REDACTED]

[REDACTED]

**11.4.3 Total Sample Size**

The total sample size required for evaluating the primary effectiveness and safety endpoints is 750 and 750 subjects respectively. Thus the total sample size is 750 for the study.

[REDACTED]

**11.5 Secondary Endpoints**

All secondary endpoints are defined in section 1.3. Among these, 4 have hypotheses to be tested. The secondary study hypotheses are:

- Severe aortic regurgitation (AR) at one year
- Kansas City Cardiomyopathy Questionnaire (KCCQ) at one year
- Moderate or severe aortic regurgitation at one year

[REDACTED]

- 6-minute walk at one year

Non-inferiority tests will be performed for each endpoint.

[Redacted]

[Redacted]

[Redacted]

[Redacted]

[Redacted]

[Redacted]

[Redacted]

[Redacted]

[Redacted]

[Redacted]

[Redacted]

[Redacted]

[Redacted]

[Redacted]

[Redacted]

[Redacted]

[Redacted]

[Redacted]

[Redacted]

[Redacted]

[Redacted]

## 11.6 Multiplicity Adjustment

[Redacted text block]

[Redacted text block]

[Redacted text block]

[Redacted text block]

[Redacted text block]

[Redacted text block]

[Redacted text block]

[Redacted text block]

[Redacted text block]

[Redacted text block]

[Redacted text block]

[Redacted]

[Redacted]

[Redacted]

[Redacted]

[Redacted]

[Redacted]

[Redacted]

[Redacted]

[Redacted]

[Redacted]

[Redacted]

[Redacted]

[Redacted]

[Redacted]

[Redacted]

[Redacted]

[Redacted]

[Redacted]

[Redacted text block]

[Redacted text block]

**11.7.4 Analysis of Descriptive Endpoints**

The descriptive endpoints listed in section 1.3 will be summarized using descriptive statistics including mean, standard deviation, median and range for continuous data and count and percentage for categorical data.

[Redacted text block]

[Redacted text block]

[Redacted text block]

[Redacted text block]

[Redacted text block]

[REDACTED]

[REDACTED]

### 11.10 Statistical Methods and Analysis (FlexNav Study, Registries and CAP)

[REDACTED]

## 12 Study Termination/Withdrawal (Pivotal IDE and CAP)

Active subject participation in the pivotal IDE is expected to last for five (5) years after index procedure unless the subject was randomized or assigned to a registry or FlexNav study but not implanted with a TAVR valve. Enrolled CAP subjects successfully implanted with a Portico valve will be followed for a minimum of one year and up to 5 years or upon study completion (whichever is reached first).

If an enrolled subject was not implanted with a TAVR valve, the following will apply:

- Randomized subjects will be followed per protocol through to the one-year visit, as part of the primary analysis intent to treat (ITT) population, and then terminated from the study.
- Registry-assigned (Roll-in or VIV Registry), FlexNav study or CAP subjects will be assessed for any adverse events through 30 days post procedure, and then terminated from the study.

The study will be closed at the investigational site following the distribution of the final clinical study report for all study locations. A copy of the final report will be provided to the IRB and Competent Authorities, if applicable, and acknowledgement requested.

Early termination of the study by either SJM or the Investigator, if applicable, will be communicated to the IRB.

Upon completion of subject participation in this study, the subject will be followed-up in accordance with institutional standards.

Possible reasons for early termination of the study and/or investigation site's participation in the study may include, but are not limited to:

- Request from the Clinical Investigation Site Principal Investigator
  - Delivery system or device fails to perform as intended
  - Occurrence of UADE which cannot be prevented in future cases
  - SJM management decision to discontinue the study
- [REDACTED]
- [REDACTED]

- Request from Regulatory bodies
- Site's noncompliance with the requirements of the CIP and/or applicable laws and regulations
- Falsification of data or any other breach of ethics or scientific principles

Subjects must be informed about their right to withdraw from the study at any time and for any reason without sanction, penalty, or loss of benefits to which the subject is otherwise entitled and withdrawal from the study will not jeopardize their future medical care or their relationship with the Principal Investigator. Subjects will be asked what the reason for termination is but have the right not to answer.

The Principal Investigator may withdraw a subject from the study at any time if s/he believes it is in the subject's best interest.

The subject's future care will not be changed by a decision, voluntary or otherwise, to withdraw from the study. All reasonable efforts should be made to retain the subject in the clinical study until completion of the clinical study.

Reasons for subject's termination or withdrawal include, but are not limited to, the following:

- Subject death (in case of subject death, cause must be documented)
- Subject and/or family request, if applicable
- Subject non-compliance
- Subject lost to follow-up, defined as the following: a subject will be considered "lost to follow-up" after a minimum of 3 documented phone calls of a physician or designee at the study site to the subject or emergency contact and a letter sent to the last known address
- Subject's participation terminated by the Principal Investigator
- Study discontinued due to management decision by sponsor or request from Regulatory bodies
- Investigational site ends participation in the study

The study will be terminated according to locally applicable regulations. If applicable, the study may be temporarily suspended or terminated, either at the local, national, or international level, at the request of the IRB and/or the FDA. Justification and request for resuming the clinical investigation after suspension will be communicated to the IRB and the FDA.

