### **7.12 Subject Withdrawal**

All living and enrolled subjects are required to complete clinical follow-up. A study subject that has been withdrawn from the study will not be replaced. All data collected up to the point of their study discontinuation will be reported and included in the data analysis as applicable.

If a subject cannot be reached for a follow-up visit, the investigator will complete a Protocol Deviation Case Report Form. The efforts undertaken to contact the subject, referring physicians, including internists as well as cardiologists, family members, or other alternate contacts should be noted in the subject's records. These efforts should include at least three (3) attempts of telephone contact on separate dates, and a registered letter before considering the subject lost-to-follow-up.

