2.3 Endpoint Analysis

2.3.1 Primary Endpoints (Randomized Cohort)

Primary Effectiveness Endpoint

The primary effectiveness endpoint is the composite endpoint of all-cause mortality or disabling stroke at one year. This endpoint will be evaluated by a non-inferiority test comparing the Portico test group to the control (CAV) group, and the primary analysis will be conducted on the ITT population. The primary analysis will be performed based on combined high and extreme risk cohort with pooled access data.

The primary analysis will be conducted on a dataset locked after all enrolled subjects have had their one-year study visit (except those withdrawn or lost-to-follow-up before one year).

Statistical Analysis Plan

[REDACTED]

[REDACTED]

[REDACTED]

[REDACTED]

[REDACTED]

[REDACTED]

Primary Safety Endpoint

The primary safety endpoint is the non-hierarchical composite endpoint of all-cause mortality, disabling stroke, life-threatening bleeding requiring blood transfusion, acute kidney injury requiring dialysis, or major vascular complications at 30 days. This endpoint will be evaluated by a non-inferiority test comparing Portico test group to the control group, and the primary analysis will be conducted on the ITT population. The primary analysis will be performed based on combined high and extreme risk cohort with pooled access data.

[REDACTED]

Statistical Analysis Plan

[REDACTED]

[REDACTED]

[REDACTED]

[REDACTED]

[REDACTED]

[REDACTED]

[REDACTED]

[REDACTED]

[REDACTED]

[REDACTED]

[REDACTED]

[REDACTED]

[REDACTED]

[REDACTED]

[REDACTED]

[REDACTED]

[REDACTED]

[REDACTED]

[REDACTED]

[REDACTED]

[REDACTED]

[REDACTED]

[REDACTED]

[REDACTED]

Statistical Analysis Plan

[REDACTED]

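### A randomized subject can be exited for non-compliance or by the investigator, and no visible text plans to ascertain death or stroke after that exit, which exposes mainly the one-year non-inferiority comparison

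*Protocol*

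**What the plan says.** Section 12 of the Protocol gives the investigator discretion to remove a subject from the study, not merely from treatment: "The Principal Investigator may withdraw a subject from the study at any time", on the condition that the investigator judges this to be best for the subject. Its list of reasons for termination or withdrawal includes "Subject non-compliance", which is not defined, and "Subject's participation terminated by the Principal Investigator".

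Three other places set what happens to the data:

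- Protocol 7.12: "All data collected up to the point of their study discontinuation will be reported and included in the data analysis as applicable". It adds: "A study subject that has been withdrawn from the study will not be replaced".
- Protocol 9.6: a death is reported "if the event occurs from the time of signed informed consent until the subject exits the study".
- SAP 2.3.1: the primary dataset locks once all enrolled subjects have had the one-year visit, "except those withdrawn or lost-to-follow-up before one year".

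Both primary endpoints are non-inferiority tests on the ITT population (SAP 2.3.1). Neither subjects nor implanters are blinded (SAP 1.6).

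Some text pulls the other way. Section 7.12 requires living enrolled subjects to complete follow-up and sets out contact efforts before a subject is called lost. Section 7.5 allows remote assessment. Section 12 asks for reasonable efforts at retention. Sections 7.3 and 12 follow randomized subjects who were never implanted to one year because they belong to the ITT population.

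**The concern.** Treatment here is a single implant, so failure to comply will mostly mean missed visits. That is no reason to stop asking whether the subject is alive or has had a stroke. Subjects who stop attending in a high- or extreme-risk population may well be sicker than those who stay, and the person deciding to withdraw them knows the valve they received.

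If the stated rules are followed, an event after exit has no planned route into the dataset. When such losses differ between arms, the one-year difference in death or disabling stroke is distorted. An analysis labelled ITT then lacks outcomes for some of the people it counts. In a non-inferiority trial, the harmful case is one where unseen events are more frequent in the Portico arm, because that makes the valves look more alike than they are.

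**Working it through.** **Reading the passages together.** Exit can come from a discretionary or undefined ground (section 12). Data are carried to the point of exit (7.12). Death reporting stops at exit (9.6). The lock does not wait (SAP 2.3.1). The never-implanted rule shows that the plan wants one-year outcomes for ITT even when treatment failed, but nothing equivalent is stated for a subject withdrawn after implant.

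**The plan's own figure.** The sample size is 750 randomized 1:1, so 750 / 2 = 375 per arm, with at least 80% power (SAP 1.5, 2.4, 2.4.3). It cannot be reproduced because the margin, alpha and assumed rates are blacked out. It can be inverted to find which margins fit. With equal true rates p:

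Δ = (z for alpha + z for 80% power) × √[2p(1−p)/375]

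- One-sided 2.5%: (1.960 + 0.842) × √(2 × 0.10 × 0.90/375) = 6.1 points at p = 10%, and 9.4 at p = 30%.
- One-sided 5%: 5.4 points at p = 10%, and 8.3 at p = 30%.

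The implied margin is therefore about 5.4 to 9.4 points. This is a consistency range, not the true margin.

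**Shift from differential withdrawal.** All inputs are assumptions. Let w be the excess share withdrawn on Portico, r the event risk after withdrawal, and count unseen events as non-events. The shift is b = w × r. When the true difference equals the margin, the chance of wrongly declaring non-inferiority is Φ(b/SE − z), with

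SE = √[p(1−p)/375 + q(1−q)/375] and q = p + Δ − b.

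Example at one-sided 2.5%, with p = 20%, Δ = 8.18 points, w = 5 points and r = 30%: b = 1.5 points, q = 0.2668, SE = 0.0308, and Φ(0.487 − 1.960) = 7.0%.

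| w (points) | r | Events hidden (375 × b) | Shift b (points) | False non-inferiority, p = 15% | p = 20% |
|---|---|---|---|---|---|
| 2 | 15% | 1.13 | 0.30 | 3.2% | 3.1% |
| 2 | 30% | 2.25 | 0.60 | 4.0% | 3.9% |
| 2 | 50% | 3.75 | 1.00 | 5.4% | 5.1% |
| 5 | 15% | 2.81 | 0.75 | 4.5% | 4.3% |
| 5 | 30% | 5.63 | 1.50 | 7.7% | 7.0% |
| 5 | 50% | 9.38 | 2.50 | 14.6% | 12.7% |

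The nominal rate is 2.5%. At one-sided 5% the same grid gives 6.1% to 23.2%.

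If withdrawn subjects were instead left out of the analysis, the shift would be about w × (r − p). With w = 5 points, r = 30% and p = 20% that is 0.5 points rather than 1.5. It changes sign if r is below p.

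**Power.** If 5% are lost equally from both arms and excluded, power = Φ(2.80 × √0.95 − 1.96) = 78%. The issue is bias, not power.

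**The 30-day endpoint.** Disabling stroke is classified by the mRS at 90 days (Appendix C), taken at a visit 90 ± 14 days after the event (7.10.1). A subject with a stroke on day 10 who is withdrawn on day 60 leaves before the assessment due around day 100, so a 30-day safety event may go unclassified.

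**The case against.** The strongest reply is that the visible text is incomplete and partly protective. Section 7.12 does not prohibit collection after exit, and section 13 reserves the sponsor's right to seek further medical documentation on enrolled subjects until the study closes. The consent form is not visible. The ITT definition (Protocol 11.1), the additional analyses of both primary endpoints (11.7.2, 11.7.3) and most of SAP 2.3.1 are blacked out and may contain censoring, imputation or sensitivity rules. The best-interest clause is conventional. Missed visits lead first to deviations, remote contact and repeated attempts, not directly to exit.

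Much of this stands, and it rules out several stronger readings that a reader might infer:

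- That the plan forbids later collection. It does not; it only fails, in what can be seen, to plan it.
- That withdrawn subjects are dropped from ITT. The SAP parenthesis governs when the dataset may lock, not who is analysed.
- That both primary endpoints are equally exposed, or that a telephone call or death register would supply them. Safety also includes bleeding, dialysis and vascular components, and disabling stroke needs an mRS by a certified rater or a neurologist or neurology fellow (Table 10). Few withdrawals are likely before day 30.
- That the bias must favour Portico. The direction is not fixed, and no document suggests more unseen events in that arm.

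What the reply does not do is close the gap. Retention efforts apply before exit, and a reserved right to documents is not planned ascertainment. A missing-data method can model uncollected deaths but cannot recover them.

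**Conclusion.** The point holds for the one-year endpoint of death or disabling stroke, and only marginally for 30-day safety. Followed as written, the visible rules leave deaths and strokes after a discretionary or non-compliance exit without a planned route into an unblinded ITT non-inferiority comparison.

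The size is illustrative. The plan gives no expected withdrawal rate, event rate or later risk, and the margin and alpha are blacked out. Under the assumed grid the hidden difference is 0.3 to 2.5 points, against an implied margin of 5.4 to 9.4. False non-inferiority at one-sided 2.5% goes from 2.5% to about 3 to 15%. The upper end needs both a 5-point excess of Portico withdrawals and a 50% later event risk, with unseen events counted as non-events. With balanced withdrawals and similar later risks the effect is small. The change should be made because it is cheap and because events not collected before the lock are hard to recover, not because a large bias has been shown.

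**What to change.** For randomized subjects, amend Protocol sections 7.12 and 12, with a matching change in 9.6:

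- Separate stopping study visits from withdrawing consent to data collection, and respect the latter fully.
- State that non-compliance or withdrawal by the investigator ends visits but not endpoint follow-up.
- Extend the death-reporting window in 9.6 to one year for subjects who only stop visits.
- For these subjects, collect vital status and any stroke through one year by telephone, treating physician or records. Obtain the 90-day mRS from a certified rater, remotely if needed.
- If exit comes before day 30, obtain the remaining safety components from records.
- Before the one-year lock, check public death records where consent and law allow.
- State in SAP 2.3.1 that these data enter the ITT primary analyses.

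The sample size does not change. The cost is protocol wording, some calls or record checks at each site, and possibly one line in the consent form.

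### Loss to follow-up has two definitions, and no visible text requires vital status to be established for lost randomized subjects before the one-year lock

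*Protocol*

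**What the plan says.** Two protocol sections describe the same status.

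- **Section 7.12 (Subject Withdrawal).** It starts from "If a subject cannot be reached for a follow-up visit", which first produces a protocol deviation form. It then asks for "at least three (3) attempts of telephone contact on separate dates, and a registered letter before considering the subject lost-to-follow-up". On other sources it says: "The efforts undertaken to contact the subject, referring physicians, including internists as well as cardiologists, family members, or other alternate contacts should be noted". Data collected up to discontinuation are kept for analysis.
- **Section 12 (Study Termination/Withdrawal).** Under "Reasons for subject's termination or withdrawal include, but are not limited to, the following", it lists loss to follow-up and sets this standard: "minimum of 3 documented phone calls of a physician or designee at the study site to the subject or emergency contact and a letter". The letter goes to the last known address.

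Two further places decide what happens next. Protocol section 9.6 makes a death reportable if it occurs between consent and the subject's exit from the study. SAP 2.3.1 locks the primary dataset once enrolled subjects have had their one-year visit, "except those withdrawn or lost-to-follow-up before one year".

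The primary effectiveness endpoint is death from any cause or disabling stroke by one year. It is tested for non-inferiority in the ITT population. SAP 1.6 states that neither subjects nor implanters were blinded.

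**The concern.** In a high and extreme risk population, death or a serious stroke is a plausible reason why nobody answers the telephone. Loss to follow-up is then related to the endpoint. With two definitions, two sites could classify the same subject differently, and the looser text is the one worded as a formal definition and tied to termination.

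Once a subject is terminated, the visible text asks for no further contact. A subject closed as lost after the 30-day or 6-month visit who dies before one year has an ITT primary event that nobody is required to look for. If the death came before closure, it is reportable, but only if someone learns of it.

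At stake is the completeness of the mortality component, which can be recovered without reaching the subject. Because the arms are unblinded, effort to retain and trace subjects could differ between them, and that would carry into the comparison.

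**Working it through.** **Step 1: the two definitions side by side.**

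| Element | Section 7.12 | Section 12 |
|---|---|---|
| Telephone attempts | At least 3, on separate dates | At least 3, dates not specified |
| Letter | Registered | Any letter to the last known address |
| Other sources | Referring physicians, family and alternate contacts (efforts to be noted) | Emergency contact |
| Link to a visit | Subject unreachable for a visit | None stated |
| Minimum time | None | None |
| Consequence | Considered lost | Reason for termination |

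A site that meets 7.12 will normally meet section 12. The reverse does not hold.

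**Step 2: the path to the endpoint.** Loss can end participation (section 12). Reportable deaths are those before exit (9.6). The lock does not wait for lost subjects (SAP 2.3.1). No visible step between these establishes vital status.

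**Step 3: the plan's figure.** The stated total is 750, or 750 / 2 = 375 per arm at 1:1, with at least 80% power. It is not disputed here. It cannot be reproduced, because alpha, event rates and margin are redacted.

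**Step 4: size of the error if lost subjects are censored.** Censoring is an inference. It rests on the general Kaplan-Meier statement in SAP 2.2.3 and on 7.12's use of data up to discontinuation. Let L be the fraction lost, f the share of the lost who died within one year, and p the event rate among those followed. Treat the lost as lost early.

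- True rate = (1 − L)p + Lf
- Estimated rate = p
- Understatement = L × (f − p)

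All three inputs are assumptions, since the documents give none: L = 1–3% (375 × 0.01 ≈ 4 to 375 × 0.03 ≈ 11 subjects per arm), f = 20–50%, p = 10–30%. Understatement in percentage points:

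| L | f | p = 10% | p = 20% | p = 30% |
|---|---|---|---|---|
| 1% | 20% | +0.1 | 0.0 | −0.1 |
| 1% | 50% | +0.4 | +0.3 | +0.2 |
| 3% | 20% | +0.3 | 0.0 | −0.3 |
| 3% | 50% | +1.2 | +0.9 | +0.6 |

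The full grid runs from −0.3 to +1.2. Pairing only the low values of L and f together and the high values together gives −0.1 to +1.2. A negative entry means the rate is overstated.

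**Step 5: if lost subjects are instead counted as event-free.** The understatement becomes L × f, from 0.01 × 0.20 = 0.2 points to 0.03 × 0.50 = 1.5 points. That is 375 × 0.01 × 0.20 ≈ 0.8 to 375 × 0.03 × 0.50 ≈ 5.6 deaths per arm.

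**Step 6: effect on the comparison.** Only the difference between arms matters. Equal L, f and p in both arms cancel. If one arm lost 3% and the other 1%, with f = 50% and p = 10% in both, the bias is 1.2 − 0.4 = 0.8 points. For scale only: with 375 per arm, 80% power and equal assumed rates of 10–30%, the margin that yields 750 is 6.1 to 9.4 points at one-sided 0.025, or 5.4 to 8.3 points at one-sided 0.05.

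**The case against.** The case against making much of this is substantial.

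- **A reader might infer that one missed visit, or three calls in one afternoon, is enough to close a subject.** The documents do not support that. Section 12 names no visit as a trigger. Under 7.12 an unreachable subject first produces a deviation form, and same-day calls would breach its requirement of separate dates. Both texts set minimums, so a site cannot choose section 12 and ignore 7.12. Section 7.5 allows remote follow-up, and section 12 asks for all reasonable efforts at retention.
- **A reader might infer that a death found after closure is not reportable.** Section 9.6 turns on the date of the event, so a death before exit remains reportable once known. Family or referring physicians would often know of it, and section 13 lets the sponsor seek further documentation.
- **A reader might read the SAP 2.3.1 exception as removing lost subjects from the analysis.** It concerns the timing of the lock only. A lost subject cannot have a one-year visit, so some such exception is unavoidable.
- **A reader might take it as stated that lost subjects are censored as event-free.** The primary method and its additional analyses are redacted, and a provision there could soften the effect.
- **The inputs to the calculation are assumed.** Under censoring the rate need not be understated, and no difference between arms is shown.

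All of this stands, and it limits the point. What it leaves untouched is that these provisions permit or encourage tracing, while none requires vital status to be established before a subject is closed or the database is locked. A death after termination falls outside section 9.6 altogether.

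**Conclusion.** The point holds as a cheap improvement. The difference between sections 7.12 and 12 is certain on the text. So is the absence of any visible vital-status requirement for randomized subjects lost before one year. It follows that a death within the year, before or after termination, can be missed in the primary effectiveness endpoint.

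The size cannot be obtained from the documents. On the assumptions above and if lost subjects are censored, the error per arm lies between a 0.3-point overstatement and a 1.2-point understatement, and it reaches the non-inferiority comparison only as far as it differs between arms. The documents do not show that loss will differ by arm or that the primary result is unsafe.

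**What to change.** 1. **Protocol sections 7.12 and 12.** Use one definition in both, on the 7.12 terms: calls on separate dates, a registered letter, and contact with referring physicians and family as a requirement. Add that contact is attempted again in the one-year window for any randomized subject listed as lost.
2. **SAP 2.3.1.** Add that, before the one-year lock, vital status is sought from medical records and public death data for every randomized subject listed as lost, as consent and local law allow. Deaths found within one year count at their date of death.

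Forbidding a declaration of loss until the one-year window closes (365 + 45 = day 410) is not needed once these two steps are in place. The search recovers deaths only. Disabling stroke depends on a modified Rankin score at 90 days (Appendix C), so it still needs contact with the subject or adequate records.

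The cost is wording in three places, modest site effort for a few subjects (about 4 to 11 per arm on the assumed loss), and possibly a slightly higher event rate. Design and sample size do not change. The consent text is not visible, so permission for public-record searches needs checking first.
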